Based on the above PK and the differential BP effects with single doses of sodium nitrate vs. nitrite, the published 10-week oral nitrite trial and preliminary findings in this combined trial, we propose to remove sodium nitrate, which is the second potential depot of nitrite. Therefore, we need to administer a greater nitrite load since the previous two sources combined (sodium nitrate and nitrite) in the first 5 subjects of this study did not result in any BP lowering (Fig 1A-C). Similar to our prior dosing modification (when we titrated from sodium nitrite 20 mg once daily to 20 mg twice daily), we propose a step-up dosing in the first 3 subjects enrolled whereby we will begin with sodium nitrite 20 mg TID daily and after 2 weeks on this dosing and if no SAE, increase to 40 mg TID for the remaining 10 weeks of the study, given the PK of the drug and to induce blood pressure lowering in our hypertensive subjects. After three subjects have completed this regimen, then we propose that from the start, all remaining subjects start on sodium nitrite 40 mg TID and continue for all 12 weeks.

Although we are increasing the dose/frequency of sodium nitrite, since we are discontinuing sodium nitrate (which is reduced to nitrite in our body as was confirmed in our Phase I PK study), we are continuing our in-person safety monitoring visits to assess for adverse events at every other week. We will continue alternating every other week phone visits to assess compliance and for adverse events. Our two safety outcomes are methemoglobin by non-invasive co-oximetry and mean arterial pressure (MAP) obtained through 3 automated resting BP measurements 30-45 min following morning nitrite dosing and averaging the final 2 of 3 MAPs.

Based on the Joint FAO/WHO ADI for sodium nitrate and nitrite, the above DASH diet patterns, and the recently observed human and rodent effects of nitrate and nitrite on blood pressure and

glucose homeostasis, including our PK/PD trial of single doses of oral nitrate and nitrite, the existing inhaled nitrite trial, and this open label trial safety and lack of BP reduction findings following a total of 5 subjects' completion, the study investigators believe that a safe and likely therapeutically effective dose of sodium nitrite will be 40 mg three times daily (~1.26 mg/kg body weight per day for a 95 kg subject). Our sodium nitrite dose selection is equivalent to 12.6 times the ADI.

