A recent study determined the safety and feasibility of prolonged intravenous nitrite infusion. Twelve adult volunteers received increasing starting doses of sodium nitrite, 4.2 to 533.8 µg/kg/hr for 48 hours. Dose limiting toxicity occurred at 445.7 µg/kg/hr (10.6 mg/kg/day) and was limited to asymptomatic transient decreases of arterial blood pressure of up to 20 mmHg and asymptomatic increases of methemoglobin levels above 5%. No tolerance or clinically significant rebound was observed³⁶. Note, this is 8.2 times the daily dose we plan to use in this trial (based on an adult body weight of 95 kg).

For nitrite, two retrospective case-control studies have shown that high maternal dietary nitrite intake from cured meat or drinking water during pregnancy might be associated with risk of childhood brain tumors and possibly gastric and esophageal cancer. This evidence is only based on retrospective case-control studies; cohort studies have found no significantly increased risks²⁴.

In the 2001 National Toxicology Program (NTP) Report summarizing 2-year rodent drinking water studies, there was no evidence of carcinogenic activity of sodium nitrite in male or female F344/N rats exposed to up to 130 mg/kg/day in males and 150 mg/kg/day in females, or in male B6C3F1 mice exposed to up to 220 mg/kg/day. There was equivocal evidence of carcinogenic activity of

sodium nitrite in the highest dose of 165 mg/kg/day in female B6C3F1 mice based on the positive trend in the incidences of squamous cell papilloma or carcinoma (combined) of the forestomach. Exposure to sodium nitrite in drinking water resulted in increased incidences of epithelial hyperplasia in the forestomach. However, no chromosomal damage (genetic toxicity) was observed in three studies conducted in rats and mice *in vivo*³⁷. Taken together, these findings suggest minimal carcinogenic nitrite-mediated risk.

In the current study, we will use much lower doses of nitrite than used safely in any of these studies. Our nitrite dose of 20 mg three times daily stepping up to 40 mg three times daily is lower than the dose used on the cardiovascular IND and <40% of the dose for cyanide poisoning.

To summarize, we anticipate the following symptoms by organ system and likely frequency of risk:

Gastrointestinal

- Common: none
- Frequent: none
- Infrequent: dry mouth
- Rare: nausea, abdominal pain, and vomiting

Hematologic

- Common: none
- Frequent: none
- Rare: methemoglobinemia

Cardiovascular

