5.4.2 Data Safety Monitoring Plan

Assuring patient safety is an essential component of this protocol. The study Investigator has primary responsibility for the oversight of the data and safety monitoring. The study sub-investigators will evaluate all adverse events. All subjects who have AEs, whether considered associated with the use of the study medication or not, must be monitored to determine the

outcome. The clinical course of the AE will be followed up according to accepted standards of medical practice, even after the end of the period of observation, until a satisfactory explanation is found or the Investigator considers it medically justifiable to terminate follow-up.

The study coordinators must view patient records for possible adverse events until 72 hours after the last dose of study drug. All untoward medical occurrences observed in subjects receiving the study drug will be recorded on the participants' adverse event case report forms (CRF) by the study coordinator under the supervision of the Investigator. The CRFs will then be reviewed for completeness and internal consistency. Subsequently, the CRFs will be recorded on an electronic password-guarded study database. The electronic database that is being used for the purpose of this study has not been fully validated to be in compliance with the FDA regulations at 21 CFR Part 11; i.e. taking into account the limited scope of this clinical investigation. In addition to internal safeguards built into a computerized system, external safeguards will be put in place to ensure that access to the computerized system and to the data is restricted to authorized personnel. Training conducted by qualified individuals on a continuing basis will be provided to individuals in the specific operations with regard to computerized systems that they are to perform during the course of the study.

The Investigator will work with the reporting sponsor and sub-investigator to prepare a detailed written summary of serious, unexpected, and treatment related adverse events, and will compare, and contrast the event with prior events. The detailed written summary will be provided to the local DSMB and the IRB.

In addition, the DSMB Report addressing the following information will be submitted to the IRB at the time of continuing review annually or more often as required:

- A list of the research personnel who participated in the data and safety monitoring.

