- The frequency of monitoring that took place during the renewal intervals and/or the dates that data and safety monitoring was conducted.
- A summary of cumulative data related to unanticipated problems (including adverse events) including a determination of causality and whether the risk to benefit assessment has changed.
- If appropriate, a summary of pertinent scientific literature reports, therapeutic developments, or results of related studies that may have an impact on the safety of study participants or the ethics of the research study.
- A summary of the outcome of reviews conducted to ensure subject privacy and research data confidentiality.
- Final conclusions regarding changes to the anticipated benefit-to-risk assessment of the study participation and final recommendations related to continuing, changing, or terminating the study.

Stopping Rule:

For safety reasons, we propose to discontinue this study protocol once 2 subjects enrolled experience one of two of the following on repeat PK testing despite appropriate nitrite dose reduction as follows:

1. Methemoglobin greater than 5%. A nitrite dose reduction is proposed from 40 mg three times daily to 20 mg three times daily if this methemoglobin % is reached at any study visit. Two hour PK testing will be repeated on a separate day at the lower nitrite dose once two subjects have reached this initial methemoglobin threshold. If methemoglobin is greater than 5% on the lower nitrite dose, participation in the study for the subject will be discontinued.
2. Mean arterial pressure (MAP) decrease <55 mmHg, or if subject's baseline MAP is <60, and there is a decrease greater than or equal to 20% from their baseline (on the morning of receiving study drug). A nitrite dose reduction is proposed from 40 mg to 20 mg three times daily if this MAP threshold is reached. Two hour PK testing will be repeated on a separate day at the lower nitrite dose once two subjects have reached this initial MAP threshold. If MAP remains <55 mmHg or in the case of the subject with a baseline MAP <60, then if MAP decrease is greater than or equal to 20% from baseline on the lower dose, subject participation in the study will be discontinued.
3. Positive pregnancy test.

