5.4.5 Reportable Adverse Events

For this study, a serious adverse event is any untoward clinical event that is thought by the investigator to be study-related, that is also:

1. Fatal or immediately life threatening
2. Permanently disabling, or severely incapacitating.
3. Requires or prolongs inpatient hospitalization.
4. Important medical events that may not result in death, be life threatening, or require hospitalization may be considered serious adverse events when, based upon appropriate medical judgment, they may jeopardize the patient, or subject, and may require medical, or surgical intervention to prevent one of the serious outcomes listed above.

If clinically important and unexpected adverse experiences, or clinically important study-related adverse experiences occur, they will be recorded on the adverse event case report form.

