5.4.6 Adverse Events Reporting Timeline

Life-threatening or fatal unexpected adverse events associated with the use of the study drug or procedures must be reported to the DSMB and the IRB within 24 hours of discovery of the incident with subsequent follow-up submission of a detailed written report.

The FDA must be notified by telephone or facsimile transmission of a human adverse event that is fatal or life-threatening no later than 7 calendar days after receiving the respective human adverse event information, followed by the subsequent submission of a written IND Safety Report.

Serious and unexpected adverse events associated with the use of the study drug or procedures must be reported to the DSMB and the IRB with subsequent follow-up submission of a detailed written report in accordance with the respective policies and procedures of the IRB. Written IND Safety Reports will be submitted to the FDA as soon as possible and, in no event, later than 15 calendar days following the investigator-sponsor's receipt of the respective adverse event information.

A summary report of the DSMB's findings will be prepared and submitted to the regulatory agencies.

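### The Stopping Rule holds back the lower-dose two-hour retest until two subjects cross the same threshold, whereas the visit procedures retest each subject who crosses

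*Combined protocol and SAP*

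**What the plan says.** **Retest.** Section 2.3.2 (the text following Visit 4) covers a subject whose methemoglobin is high or blood pressure low at Visit 4 or later. The dose is halved to 20 mg three times daily, that subject repeats the two-hour monitoring on the lower dose, and leaves the study if the problem persists. No second subject is needed. Section 3.2 agrees: it allows exclusion for a low MAP that is still present when that subject's PK test is repeated on the lower dose.

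The Stopping Rule in section 5.4.2 also halves the dose at once. Item 1 concerns methemoglobin above 5%. Item 2 concerns MAP below 55 mmHg, or a fall of at least 20% where baseline MAP is under 60. The two-hour retest then follows on a separate day, but only "once two subjects have reached this initial methemoglobin threshold"; item 2 sets the same condition for MAP. The protocol is discontinued when two subjects fail either criterion on that repeat PK test. A closing paragraph separately halts the study, pending board review, for an unexpected death or a listed event that occurs despite dose reduction.

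**Serious adverse events.** Section 5.4.5 defines one as "any untoward clinical event that is thought by the investigator to be study-related" that also meets a seriousness criterion. Section 2.2.2 uses the term as a gate for the first three subjects: "after 2 weeks on this dosing and if no SAE, increase to 40 mg TID". Section 5.1.1 still describes "20 mg three times daily stepping up to 40 mg three times daily". Elsewhere relatedness is kept apart from the event. Section 5.4.2 says "All subjects who have AEs, whether considered associated with the use of the study medication or not, must be monitored", and its board report summarises "unanticipated problems (including adverse events) including a determination of causality". Section 5.4.6 names association as a further condition: "Serious and unexpected adverse events associated with the use of the study drug or procedures must be reported to the DSMB".

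**The concern.** The two retest instructions cannot both be followed when one subject has crossed a threshold. Staff working from 2.3.2 would bring that subject back for a two-hour session on the lower dose; staff working from 5.4.2 would wait for a second crosser of the same threshold. The formal two-subject stop counts only repeat-test results, so the Stopping Rule can withhold the measurement on which it depends.

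The secondary point is that the gate on the step-up rests on a term that already contains a causality judgement. In an open-label, single-arm study the investigator makes that judgement without a control group. Read literally, a hospital admission in the first two weeks that is judged unrelated does not stop the dose being doubled.

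**Working it through.** **1. A lone crosser under each text**

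| | Section 2.3.2 | Section 5.4.2 |
|---|---|---|
| Dose | halved | halved |
| Two-hour retest | this subject's own crossing | a second subject crosses the same threshold |
| Blood pressure after the lower dose | every 15 min for 2 h: 120/15 = 8 time points | 3 readings, 5 min apart, from 0.5 h, at in-person visits |
| Methemoglobin after the lower dose | 0.5, 1 and 2 h | one value per in-person visit |
| Subject leaves if | problem persists on lower dose | problem persists on lower dose |

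The right-hand column applies until Visit 17, which has its own two-hour session.

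A subject who crosses at Visit 4 (Day 1) is next scheduled in person at Visit 6 (Day 15 ±7). That is nominally 14 days, or 14 × 3 = 42 doses, unless the subject is recalled earlier under section 2.2.4. Section 2.3.2 gives no date for its retest, so the difference in delay cannot be stated exactly.

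Section 2.2.2 reports peak plasma nitrite at 30 minutes and a half-life of about 40 minutes, so the in-person reading falls near peak exposure. It also reports a blood pressure decline over 3 hours after 20 mg, so one early set of readings need not catch the lowest MAP.

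**2. The formal stop**

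- *Case (a): one methemoglobin crosser and one MAP crosser.* Neither item reaches two, so 5.4.2 triggers no retest. Under 2.3.2 both are retested and, if both fail, they make up the two subjects.
- *Case (b): a first crosser completes 12 weeks before a second subject crosses the same threshold.* Under 5.4.2 the first can no longer be retested on treatment.
- *Exactly one crosser.* The two-subject stop cannot be met under either text.

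**3. Size, on assumed rates**

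The documents give no crossing rate, and 2.3.2 calls the event rare. With n = 30 and an assumed per-subject rate p for one threshold:

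- Lone crosser: 30·p·(1−p)^29
- Case (a), equal and independent rates for the two thresholds: 30·29·[p(1−p)]²·[(1−p)²]^28
- Two or more crossers of the same threshold: 1 − (1−p)^30 − 30·p·(1−p)^29

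| p | Lone crosser | Case (a) | Two or more, same threshold |
|---|---|---|---|
| 0.1% | 2.9% | 0.08% | 0.04% |
| 0.5% | 13.0% | 1.6% | 1.0% |
| 1% | 22.4% | 4.9% | 3.6% |
| 2% | 33.4% | 10.8% | 12.1% |

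The case (a) column is a ceiling on a changed stop by that route, because both subjects must also fail at 20 mg. With unequal assumed rates of 0.5% for methemoglobin and 0.1% for MAP it is 870 × (0.005 × 0.999) × (0.001 × 0.995) × (0.995 × 0.999)^28 ≈ 0.4%.

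For case (b), suppose exactly two subjects cross the same threshold and starts are evenly spaced (no accrual rate is given). Of the 435 pairs, the 12-week periods do not overlap in 378 (87%) at one start a month, 300 (69%) at two and 171 (39%) at four. Here too, a changed stop requires both to fail at 20 mg.

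**4. The step-up gate**

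If a fraction q of serious events is judged related and the assumed two-week serious-event rate is s, the gate acts at least once in three subjects with probability 1 − (1 − sq)³. At s = 5% this is 14.3% without the relatedness clause (q = 1) and 7.3% with q = 0.5. At s = 10% it is 27.1% and 14.3%.

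**The case against.** A reader might infer that a lone crosser never has a two-hour test on the lower dose. That goes too far. Visit 17 gives every completer two hours of blood pressure and methemoglobin measurements. The Visit 17 text names only the 40 mg dose, so testing a reduced-dose subject at 20 mg is an interpretation, though a natural one. That session comes at week 12, only in completers, and the plan does not say that it counts as a repeat PK test. What remains is delay and ambiguity, not a complete absence of testing.

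A reader might also infer that discontinuation for low MAP lacks its test, or that one subject's failure cannot interrupt the study. Neither holds. Item 2 acts on MAP on the lower dose and does not itself demand a PK session, and MAP is read 30 to 45 minutes after dosing at in-person visits. The closing paragraph of the Stopping Rule can halt the study for board review without a second subject, although its count of three events is unclear against a list of four items.

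The rates are weak evidence. Section 5.1.1 says that none of 80 volunteers exceeded 3% methemoglobin at doses below 75 mg, which gives an upper bound of 1 − 0.05^(1/80) = 3.7%. That bound concerns 3%, not the trial's 5%, and says nothing about MAP. Section 2.2.2 cites a 10-week oral trial with methemoglobin changes never above 3% and no clinically significant change in resting pressure. At 130/85 the MAP is 85 + 45/3 = 100, so reaching 55 needs a fall of about 45 mmHg, against cited falls of 7, 11 to 14, and up to 20. Equal rates for the two thresholds are therefore implausible, and the equal-rate column for case (a) should be read as generous.

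On serious events, gating escalation on related events is a recognisable choice, and the association condition in 5.4.6 may be redundant with 5.4.5 rather than contradict it. The clause reaches only three subjects, and the documents do not say whether they have already been treated. It does not suppress safety capture: all adverse events are followed, and the rule beginning "The FDA must be notified by telephone or facsimile transmission of a human adverse event that is fatal or life-threatening" carries no relatedness condition in its wording.

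**Conclusion.** The point holds as a conflict between two operative instructions. Section 5.4.2 makes the lower-dose retest wait for a second crosser of the same threshold; section 2.3.2 does not, and section 3.2 presumes the subject's own repeat test. A lone crosser then lacks a prompt two-hour retest, and the formal two-subject stop can miss or delay counting subjects in cases (a) and (b). First-line dose reduction, discontinuation on visit readings and the halt pending board review are intact, so this should be fixed but does not leave subjects unprotected.

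The conflict follows from the text and needs no rate. Its frequency cannot be derived from the documents; the percentages above are illustrations that depend on the assumed rates, on independence and, for case (b), on assumed accrual. The serious-event clause is a correct but secondary observation, confined to the step-up in the first three subjects.

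**What to change.** In items 1 and 2 of the Stopping Rule (5.4.2), replace the two-subject condition on the retest with: in each subject who reaches this threshold. This matches 2.3.2. The two-subject count for stopping the study can stay.

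In 5.4.5, delete the clause on the investigator's view of relatedness and record relatedness as a separate field.

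The cost is a wording amendment with DSMB and IRB sign-off. The per-subject retest is already planned in 2.3.2, so it adds no new procedure. The drawback of the second change is that a clearly unrelated serious event could hold the step-up in one of the first three subjects. Under 5.4.6, reporting of serious unexpected events to the DSMB and IRB would remain conditional on association.

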5.4.6 Adverse Events Reporting Timeline

Life-threatening or fatal unexpected adverse events associated with the use of the study drug or procedures must be reported to the DSMB and the IRB within 24 hours of discovery of the incident with subsequent follow-up submission of a detailed written report.

The FDA must be notified by telephone or facsimile transmission of a human adverse event that is fatal or life-threatening no later than 7 calendar days after receiving the respective human adverse event information, followed by the subsequent submission of a written IND Safety Report.

Serious and unexpected adverse events associated with the use of the study drug or procedures must be reported to the DSMB and the IRB with subsequent follow-up submission of a detailed written report in accordance with the respective policies and procedures of the IRB. Written IND Safety Reports will be submitted to the FDA as soon as possible and, in no event, later than 15 calendar days following the investigator-sponsor's receipt of the respective adverse event information.

A summary report of the DSMB's findings will be prepared and submitted to the regulatory agencies.

5.5 RISKS MANAGEMENT PROCEDURES

5.5.1 Protection Against Risks

General Risks of Study Protocol and Procedures

All research interventions/activities will be conducted in private patient care areas. The collection of sensitive information about subjects is limited to the amount necessary to achieve the aims of the research, so that no unneeded sensitive information is being collected.

All demographic and clinical information about the subject will be stored on an electronic password-guarded study database under the supervision of the Investigator for this protocol. The electronic database that is being used for the purpose of this study has not been fully validated to be in compliance with the FDA regulations at 21 CFR Part 11; i.e. taking into account the limited scope of this clinical investigation. The data will be stripped of individual identifiers and stored anonymously with a subject number. Information linking subject identifiers with the coded subject number will be stored under password protection on computers in locked areas, with access only to the database manager. Maintaining records in locked files in locked offices will protect confidentiality of subjects. All staff will sign confidentiality statements. Access to the database will be limited to the data manager and staff under the supervision of the Investigator.

Specimens will be stripped of subject identifiers and stored according to a similar coding protocol as described above. These specimens will be stored safely in the custody of the Investigator responsible for the individual assays. The Investigators will limit future access to any remaining sample to only those investigators with prior IRB approval for their studies.

All staff involved in this study are properly credentialed and instructed in the areas of testing, confidentiality, and safety.

The Investigator will retain the data for the entire period of this study. The Investigator may continue to use and disclose subjects' de-identified information for the purpose of this study for a minimum of seven years after final reporting or publication of the study. If the subject and/or legal representative decide to withdraw or be withdrawn from study participation, they may request that the study data and samples be destroyed.

